15.5.3 Donor Specific Antibody Tests

Serum samples for donor specific antibody testing will be collected at Screening, and at Visits 4, 6, and 9. A by-patient listing of all results will be provided.

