## 10.2 Patient Exclusion Criteria

1. Patients with confirmed other causes for loss of lung function, such as acute infection, acute rejection, restrictive allograft syndrome (CLAD – RAS phenotype, see Protocol Specific Definitions),etc.
2. Patients with acute antibody-mediated rejection at Screening. In this context, clinically stable patients (as judged by the Investigator) with detectable levels of donor specific antibodies (DSA) at the Screening Visit are eligible for the study
3. Active acute bacterial, viral, or fungal infection not successfully resolved at least 4 weeks prior to the Screening Visit. Patients with chronic infection or colonization who are clinically stable as per judgement of the Investigator are eligible for the study.
4. Mechanical ventilation (including CPAP) within 12 weeks prior to Randomization.
5. Patients with uncontrolled hypertension.
6. Patient has baseline resting oxygen saturation of < 89% on room air or use of supplemental oxygen at rest.
7. Evidence of functional airway stenosis (e.g., bronchomalacia/tracheomalacia, airway stents, or airways requiring balloon dilatations to maintain patency) with onset after the initial diagnosis of BOS and ongoing at Screening and/or Baseline Visit.
8. Known hypersensitivity to L-CsA or to cyclosporine A.
9. Patients with chronic renal failure defined as serum creatinine > 2.5 mg/dL at screening, or requiring chronic dialysis.
10. Patients with liver disease and serum bilirubin > 3-fold upper limit of normal range or transaminases > 2.5 upper limit of normal range.
11. Patients with active malignancy within the previous 2 years, including post-transplant lymphoproliferative disorder, with the exception of treated, localized basal and squamous cell carcinomas.
12. Pregnant women or women who are unwilling to use appropriate birth control to avoid pregnancy through their End of Study Visit.
13. Women who are currently breastfeeding.
14. Receipt of an investigational drug as part of a clinical trial within 4 weeks prior to the Screening Visit. This is defined as any treatment that is implemented under an Investigational New Drug (IND) or compassionate use.
15. Patients who have received extracorporeal photophoresis (ECP) for treatment of BOS within 1 month prior to Randomization.
16. Patients who are currently participating in an interventional clinical trial.

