## 27 APPENDIX III – ANTIBODY-MEDIATED REJECTION

Key diagnostic criteria include the presence of antibodies directed toward donor human leukocyte antigens and characteristic lung histology with or without evidence of complement 4d within the graft. Exclusion of other causes of allograft dysfunction increases confidence in the diagnosis but is not essential. Pulmonary AMR may be clinical (allograft dysfunction which can be asymptomatic) or sub-clinical (normal allograft function). Both clinical and sub-clinical AMR were further sub-categorized into 3 mutually exclusive possibilities (definite, probable and possible). These categories were based on the degree of certainty related to the presence or absence of a number of pathologic, serologic, clinical and immunologic criteria (Table 8 and [Table 9](#)).

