11 DEMOGRAPHICS AND BASELINE CHARACTERISTICS, AND DISEASE AND MEDICAL HISTORY

11.1 Demographic and Baseline Characteristics

All demographic, baseline characteristics, including azithromycin at randomization, and antibody-response data will be summarized by treatment group for SAF, FAS and PPS. For summary purposes, the most recent, non-missing result obtained on or prior to the baseline visit will be used.

Azithromycin at randomization will be derived by identifying azithromycin among medications collected in the study (generic name: azithromycin) using any of the following rules:

- azithromycin is ongoing at the date of randomization (regardless of start date)
- azithromycin start date is on the randomization date (regardless of end date)

By-patient listings will be provided for all demographic and baseline characteristics.

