15.5.2 Blood Sampling CNI/mTOR Inhibitors

A whole blood sample for the determination of blood sampling calcineurin inhibitor/mammalian target of rapamycin (CNI/mTOR) inhibitors, where for CNI, cyclosporine A and/or tacrolimus trough level will be collected at each visit. In patients allocated to L-CsA plus SoC, the sample should be collected 60 min before L-CsA inhalation. Blood samples will be evaluated by the local laboratories associated with each site. The summaries described in this section will be presented relative to baseline, defined as the most recent, non-missing result on or before the date of randomization. No imputation for missing data will be performed.

All CNI/mTOR data reported in the eCRF will be presented in by-patient listings. Descriptive statistics of observed values and changes from baseline will be presented by visit and treatment group.

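### In the readable SAP, donor-specific antibody results after baseline appear only in a patient listing, although the protocol promises a descriptive between-arm comparison of safety measures

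*SAP*

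**What the plan says.** Protocol 13.1.5.3 and SAP 15.5.3 give the same sampling schedule. In the SAP, serum samples for DSA testing are "collected at Screening, and at Visits 4, 6, and 9. A by-patient listing of all results will be provided". The second of those sentences is the only output that SAP 15.5.3 plans.

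SAP 11.1 adds that "antibody-response data will be summarized by treatment group for SAF, FAS and PPS", but for that summary "the most recent, non-missing result obtained on or prior to the baseline visit will be used". Protocol 15.2.2 likewise places antibody-response data under baseline comparability.

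The section just before the DSA one, SAP 15.5.2 on calcineurin and mTOR inhibitor levels, plans a listing and also a by-arm summary: "Descriptive statistics of observed values and changes from baseline will be presented by visit and treatment group".

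Two protocol passages explain why DSA is collected and how it has to be read. Appendix III says of antibody-mediated rejection: "Key diagnostic criteria include the presence of antibodies directed toward donor human leukocyte antigens". In its Table 9, DSA without histology or C4d already counts as possible sub-clinical rejection. The exclusion criteria in Section 10.2 state that clinically stable patients "with detectable levels of donor specific antibodies (DSA) at the Screening Visit are eligible for the study".

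**The concern.** DSA testing sits in the protocol's safety chapter. Protocol 15.2.5 points to Section 13.1 for the list of safety outcomes and commits to a descriptive comparison of the arms for all of them. Protocol 15 also makes the final SAP the analysis of record where the two documents differ, so the narrower SAP text governs. On what can be read, the arms are compared on antibodies before treatment and not after it.

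At stake is one immunological safety comparison that the protocol promises, in an open-label trial of an added immunosuppressant. A listing can be read patient by patient. It does not say who counts as newly positive or out of how many, and any count made from it later would rest on a rule chosen after the results were seen.

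**Working it through.** **1. Trace each scheduled DSA time point to its output.**

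| Time point | By-arm summary in readable text | Listing |
|---|---|---|
| Screening | Yes (SAP 11.1) | Yes (SAP 15.5.3) |
| V4, Week 12 | None found | Yes |
| V6, Week 24 | None found | Yes |
| V9, Week 48 | None found | Yes |

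Three of the four time points have a listing only.

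**2. Compare the neighbouring sections.** SAP 15.5.1 (hematology and biochemistry) and 15.5.2 (drug levels) plan listings plus statistics by visit and arm. Within SAP 15.5, only pregnancy tests (15.5.4) share the listing-only treatment. Physical examinations (15.8) are also listed only.

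**3. Compare protocol and SAP.** The chain is Protocol 15.2.5, then Section 13.1, then 13.1.5.3 (DSA). The protocol's promise therefore covers DSA. The readable part of SAP 16, which lists changes from the protocol, has no entry on DSA.

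**4. Ask whether a listing yields the comparison.** Patients may enter DSA-positive, so a later positive may be new or carried over. The quantity of interest in each arm is

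newly positive proportion = (negative at Screening and positive at V4, V6 or V9) / (negative at Screening and tested at least once afterwards).

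No readable passage defines a positive result, the numerator or the denominator.

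**5. Gauge the precision of such a table.** The plan gives no DSA figure to reproduce; its power statement concerns FEV1 only. SAP 8.2 reports 62 patients randomized and SAP 7.2 gives 1:1 allocation, so about 62/2 = 31 per arm. For a common new-positive rate p, which is assumed because the documents give none, the 95% half-width of the risk difference is 1.96 × √(2p(1−p)/31):

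| Assumed p | 2p(1−p)/31 | Half-width |
|---|---|---|
| 5% | 0.00306 | 11 points |
| 10% | 0.00581 | 15 points |
| 20% | 0.01032 | 20 points |
| 30% | 0.01355 | 23 points |

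These widths are optimistic, because Screening-positive and untested patients leave the denominator. The approximation is rough at 5%, where 31 × 0.05 gives only about 1.6 expected events per arm. A two-sided 5% test at 31 per arm would have about 19% power for 10% versus 20% and about 50% for 10% versus 30%. That supports a descriptive table without a test.

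**The case against.** **Redaction.** A reader might infer that new DSA is never compared between arms. The documents do not support that. SAP 14.3 and 14.4 are blacked out, and the version history shows that 14.4 runs to at least 14.4.9. Protocol 12.1.6 and 12.1.7 place acute and antibody-mediated rejection among the efficacy assessments, so the redacted pages are a natural home for such an analysis. This stands, and it limits the finding to the readable text.

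**Harm mechanism.** A reader might also infer that new DSA is where harm would first show if systemic immunosuppression were lowered more in the L-CsA arm. The documents make DSA a diagnostic criterion and say nothing about its being the earliest sign. The creatinine provisions in Protocol 11.3.1 apply to both arms, and Protocol 9.2 expects no dose reductions because of L-CsA. Any divergence would be visible anyway: SAP 12.1 summarizes immunosuppressant doses by arm and interval, and SAP 15.5.2 summarizes drug levels by arm and visit. Rejection reported as an adverse event would enter the by-arm tables of SAP 15.3. All of this stands, although none of it counts new DSA.

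**General rules.** SAP 8.1 calls for by-visit tabulations comparing the groups, and SAP 9.2.1 speaks of summarizing all safety data. Neither names DSA, and SAP 15.5.3 is the more specific text. If the general rules are meant to apply, 15.5.3 should say so.

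**Small trial.** With 62 patients, and data listed by patient and treatment group (Protocol 15), someone could count by hand. That is true, but without a stated rule the count is post hoc. It is also true that DSA is neither a named safety endpoint nor in the parameter list of Protocol 13.1.5, and that SAP 14 describes all analyses as descriptive. This bears on severity.

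**Conclusion.** The point holds in a limited form. In the readable text, DSA results at V4, V6 and V9 are listed by patient and not summarized by arm. That is narrower than the comparison promised in Protocol 15.2.5, and the readable part of SAP 16 does not declare it.

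The conclusion rests on two assumptions: that the redacted parts of SAP 14.3 and 14.4 hold no by-arm DSA table, which cannot be checked, and that SAP 15.5.3 overrides the general rule in SAP 8.1.

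Severity is minor. The data are already collected, no trial conclusion depends on them, and at about 31 per arm only large differences could be distinguished from chance. The gain is a pre-specified count in place of one improvised from a listing.

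**What to change.** In SAP 15.5.3, add one descriptive table on the safety analysis set, by arm:

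- At Screening, V4, V6 and V9: number tested, and number (%) DSA-positive among those tested.
- Number (%) newly positive at any post-baseline visit, among patients negative at Screening and tested at least once afterwards.
- Screening-positive patients shown separately, as persisting or cleared.

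State the definition of a positive result before database lock, for example the local laboratory's call as recorded. Say also that a test from the 4 weeks before Screening, which Protocol 13.1.5.3 accepts, counts as the Screening result. Showing the number tested matters because V4 and V6 may be held remotely, and the remote-visit column of the Schedule of Activities has no DSA test.

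No hypothesis test is needed. If a confidence interval is shown, label it descriptive, consistent with SAP 15.1. If the redacted sections already contain this analysis, a cross-reference from 15.5.3 is enough. If listing-only is intended, record it in SAP 16 as a change from Protocol 15.2.5.

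The cost is one table from existing data, with no change to sample size, error rate or patient care. The downside is that local assays and cut-offs differ. A positive/negative call does not remove that noise, and the counts will be small.

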15.5.4 Pregnancy Tests

Serum samples from women of childbearing potential will be collected for pregnancy. A by-patient listing of all results will be provided.

15.6 Renal Function

In addition to the summarization of serum creatinine as described in previous section, renal dysfunction will be further listed and summarized by treatment group based upon the classification of AEs with the following PTs (see protocol section 13.1.5.4, Table 7 and SAP section 16):

- Blood Creatinine Increased,
- Renal Impairment,
- Renal Failure,
- Acute kidney injury,
- Azotaemia,
- Chronic kidney disease,
- Proteinuria,
- Renal disorder.

15.7 Vital Signs

Vital signs will be assessed at each visit. The following vital signs will be recorded:

- Systolic and diastolic blood pressure (sitting, after 5 minutes of rest);
- Heart rate (sitting, after 5 minutes of rest);
- Body temperature (the same method should be used for each patient and throughout the trial);
- Respiratory rate;
- Weight.

The summaries described in this section will be presented relative to baseline, defined as the most recent, non-missing result on or before the date of randomization. No imputation for missing data will be performed.

Descriptive statistics of observed values and for changes from baseline will be presented by visit and treatment group on SAF. Vital signs data reported in the eCRF will be presented in by-patient listings.

15.8 Physical Examination

A physical examination will be carried out at Screening and every subsequent visit.

The following body systems will be examined: body weight, cardiovascular, respiratory, nervous, gastrointestinal, hepatic, renal, dermatological, musculoskeletal, extremities, eyes, ears, nose, throat, and lymphatic. Patient height will be measured at Screening Visit only.

All physical examination data, including abnormal findings reported in the eCRF will only be presented in by-patient listing.

16 Changes from Planned Analyses

The following changes from protocol were made.

- The SAF population has been further detailed to better define the actual treatment received by patients.
- CCI
[REDACTED].
- CCI
[REDACTED]
[REDACTED]
[REDACTED]
- The protocol amendment version 5.0 Table 1 displaying the 2019 CLAD staging has been amended in this SAP. Table 6 shows the correct descriptions for the 2019 CLAD Staging as reported in Verleden et al., 2019 [3].
- CCI
[REDACTED]
[REDACTED]
- In section 9.4 further details compared to protocol have been added for handling visits that have more than one accepted spirometry assigned, with some of them performed after IMP inhalation.
- The protocol amendment details the hypothesis to assess for superiority of the L-CsA plus SoC to SoC alone in preserving FEV1, i.e., under H1 it is expected that patients treated with L-CsA plus SoC will exhibit a smaller mean FEV1 decline between baseline and the end of Week 48 than those who receive SoC alone. However, due to the decrease in sample

L-CsA:

Treatment of BOS after SLT

Protocol Number:

BT – L-CsA – 301 – SLT

Sponsor:

Zambon SpA

size then the study will be underpowered to assess the statistical hypothesis, and therefore the primary analysis will be descriptive in nature. **CCI**

- **CCI**

- BOS Progressions will be evaluated up to last assessment, even after treatment discontinuation or completion.
- Additional PTs will be included in the definition of renal dysfunction. In addition to AEs listed in the protocol (Blood Creatinine Increased, Renal Impairment, and Renal Failure), the following AEs will be considered: Acute kidney injury, Azotaemia, Chronic kidney disease, Proteinuria, and Renal disorder.

L-CsA:

Treatment of BOS after SLT

Protocol Number:

BT – L-CsA – 301 – SLT

Sponsor:

Zambon SpA

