## 9.6 Stopping rules and Discontinuation Criteria

### 9.6.1 Patient Level

#### Regular termination of clinical trial participation:

The investigational treatment will be terminated after 48 weeks (End of Treatment [EoT]). The treatment period will be followed by a follow-up of 4 weeks' duration (End of Study [EoS]). Patients who enroll in Clinical Trial BT – L-CsA – 303 – FU (BOSTON-3) will forego the 4-week follow-up period of BOSTON-1 and will enroll directly into BOSTON-3 at the Week 48 Visit. For these patients, the EOT visit will be the EOS visit.

Any patients with ongoing SAEs will be followed-up until recovery or stabilization of the SAE. If a patient has enrolled in BOSTON-3, pharmacovigilance will be continuously assessed in the scope of the follow-up clinical trial.

Premature termination of clinical trial participation:

- Patients may discontinue participation in the clinical trial at any time by revoking their informed consent.
- The Investigator may withdraw a patient at any time if it is in the best interest of the patient based upon clinical assessments.
- Patient is lost to follow-up
- Re-transplantation. Patients who are eligible for and/or listed for re-transplantation will continue to participate in the trial until they receive re-transplantation surgery.
- Pregnancy (the patient will be followed via a pregnancy registry)
- Zambon SpA may choose to terminate the study at a site or as a whole for reasons such as, but not limited to, medical futility, safety concerns, or poor study site performance.

Patients stopping to take study treatment but not revoking their consent will be encouraged to continue the visits planned until the scheduled end and perform all the important safety and efficacy assessments for the full duration of the study.

If the patient to return for clinical follow-up, the patient will be contacted by telephone or a letter will be sent requesting a mandatory clinic visit and the reason for non-compliance will be documented.

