#### 12.1.2 Progression of BOS

Due to the patchy distribution of affected areas in the pulmonary allograft, chronic rejection and BOS are not uniformly detectable by biopsy. This method has turned out to be too unspecific and harmful for routine diagnostic use. Therefore, non-invasive spirometry has been routinely

---

established using standardized airflow measurements which nowadays is used to determine FEV1 as a surrogate marker for the diagnosis of BOS, its classification and its control of progression.

Progression of BOS during the treatment period is defined as a decline of FEV1 of  $\geq 10\%$  or  $\geq 200$  mL from Baseline FEV1 and absolute decrease in FEV1/FVC of  $> 5\%$  that is confirmed by measurements that are taken with **CCl** spirometer at least 2 weeks apart OR worsening in BOS Severity grade OR Re-transplantation, OR Death from respiratory failure.

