EQ-5D-5L			X			

NOTE: The Screening phase (time between screening and randomization visit) last from one day to up to 4 weeks.

 Conduct prior to any screening activities.

 Not more than 7 days prior to Randomization. Urine pregnancy test is allowed at Visit 1 only. Austria only: Urine pregnancy tests will be performed every month according to local law (Visits 5 through 9).

 Including body weight, height (Screening Visit only), cardiovascular, respiratory, nervous, gastrointestinal, hepatic, renal, dermatological, musculoskeletal, extremities, eyes, ears, nose, throat, and lymphatic.

 Including systolic and diastolic blood pressure (sitting, after 5 minutes of rest), pulse rate (sitting, after 5 minutes of rest), body temperature (the same method should be used for each patient and throughout the clinical trial), and respiratory rate.

 At all visits, spirometry will be performed on the CCI and on the CCI as per Section 12.1.1. At the Baseline Visit (V1), serial spirometry is to be performed prior to Randomization (CCI and CCI; CCI only), and (CCI; CCI only) after completion of L-CsA dose (or after Randomization to SoC). Remote visits will be performed using the CCI device only. Visit 10 spirometry will be performed in those patients not rolling over to Boston 3 on the CCI only.

 Only in patients randomized to receive L-CsA treatment.

[figure not shown]
 within 60 minutes prior to next CNI administration. Blood levels of mTor inhibitors will be taken only if applicable, i.e., if patient is treated with mTor inhibitors.

 ±3 days of the Visit date.

 If a DSA test performed within 4 weeks before screening is available, a further DSA test at screening visit will not be mandatory.

 Laboratory tests at V1 are not mandatory in case laboratory tests at screening visit have been performed within 2 weeks from V1.

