08 May 2024	3.0	Section 9.2.1 has been modified to clarify the definition of actual treatment in the SAI population.

	
Additional explanations have been added in Section 12.1 to clarify the calculation of intervals between visits.
 
The definition of BLAD has been fixed in section 11.3.
 
CCI Section 14.1.1 has been amended to consider a treatment composite strategy instead of a treatment policy one. Therefore, death and re-transplantation IE are included in the endpoint through an imputation of FEV1 as a treatment failure (FEV1 equal to zero). This applies also to 14.1.3, 14.2.1, 14.2.2, 14.3.1, and 14.4.6.
 
In Section 14.2.1 a ranked ANCOVA has been planned in case of violation of normality assumption even after log-transformation of data.
 
Clarifications in section 14.2.5.1, 14.3.2, 14.4.1, and 14.4.9 have been added to specify analysis, comparisons, and figures. It is clarified in section 14.3.2 that BOS progressions will be considered up to study end, even after treatment completion/discontinuation.
 
It is specified in section 14.4.1 that in case of not enough responses for using logistic regression, then exact methods will be used for CI and test.
 
Sensitivity analyses have added in sections 14.4.2 and 14.4.3.
 
Additional subgroup analyses (by use of azithromycin at baseline and by BLAD disease at baseline) have been added in Section 14.5. The BLAD definition has been added in section 11.3.
 
In section 15.2 more instructions for the analysis of Extent of Exposure have been added, while in Section 15.3.1 it has been added an analysis of infection rates by year and overall.

--	---

L-CsA:

Treatment of BOS after SLT

Protocol Number:

BT – L-CsA – 301 – SLT

Sponsor:

Zambon SpA

		
Section 15.5.1 has been updated with the full list of Hematology and Biochemistry exams.
 
Section 15.6 has been updated to include more PTs.
 
Minor errors in the CCI [REDACTED] have been fixed in section 17.

--	--	--

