7 INVESTIGATIONAL PLAN

7.1 Trial Design

This is a Phase III, prospective, multicenter, randomized, controlled clinical trial of L-CsA for the treatment of BOS in adults with clinically defined BOS (Chronic Lung Allograft Dysfunction (CLAD) – BOS phenotype) following SLT. Patients will receive either L-CsA (5 mg) via the **CCI** SoC treatment or SoC alone, for a period of 48 weeks. All patients will be eligible to continue in an open-label extension trial of L-CsA, BT – L-CsA – 303 – FU (BOSTON-3) following completion of BOSTON-1.

A total of 11 visits (Screening, V1 through V10) will be performed during the clinical trial. After informed consent has been obtained, a Screening Visit will be carried out in order to check general eligibility for participation. If a patient fails the screening process due to not meeting inclusion/exclusion criteria, a re-screening is allowed. At the Baseline Visit (V1, randomization visit), inclusion and exclusion criteria will be re-checked, and baseline serial spirometry will be performed. During the 48-week treatment period, visits are scheduled every 4-8 weeks (V2, ..., V9). Visit 9 (End of Treatment, EoT) is scheduled to occur 48 weeks after Visit 1. If a patient has an event that meets one of the criteria for progression of BOS, progression of BOS must be

confirmed by measurements that are taken with CCI [REDACTED] spirometer at least 2 weeks apart. Visit 10 (End of Study, EoS) is a safety follow-up visit performed 4 weeks after Visit 9/EoT only in patients not rolling over to the extension study (BOSTON-3) or if possible, in patients who decided to withdraw the consent during the study. For patients who will enroll to BOSTON-3, the EoT visit will be the EoS visit.

However, if one of the visits from Visit 2 to Visit 8 and discontinuation visits cannot be performed at site due to COVID-19, remote visits (e.g., by telephone) are possible.

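### Counting BOS progression past Week 48 makes scheduled confirmation of a Visit 9 fall depend on entry into the open-label extension

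*SAP*

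**What the plan says.** **Counting period.** Protocol 12.1.2 begins: "Progression of BOS during the treatment period is defined as a decline". SAP section 16 changes this: "BOS Progressions will be evaluated up to last assessment, even after treatment discontinuation or completion". The SAP version history for version 3.0 describes the same change to section 14.3.2: "BOS progressions will be considered up to study end, even after treatment completion/discontinuation". Section 14.3.2 itself is blacked out in the public SAP.

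**Confirmation.** In Protocol 12.1.2 the FEV1 and FEV1/FVC criterion must be confirmed by measurements "at least 2 weeks apart OR worsening in BOS Severity grade OR Re-transplantation, OR Death from respiratory failure". Read literally, the last three components need no confirmation. SAP 7.1 instead asks for confirmation of an event meeting any one of the criteria.

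**Who is seen after Visit 9.** A footnote to the protocol's Schedule of Activities says: "Visit 10 spirometry will be performed in those patients not rolling over to Boston 3". Protocol 14.2.5 and SAP 7.1 add patients who withdraw consent, if possible. Of BOSTON-3 entrants, Protocol 9.6.1 says: "For these patients, the EOT visit will be the EOS visit".

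**Context.** Patients and treating physicians know the arm, and both arms may enter BOSTON-3, where L-CsA is given. Default censoring for time-to-event variables is at study termination (SAP 8.1). Drop-outs for other reasons are treated as non-informative (SAP 9.5.1). The investigator, not the blinded committee, has the final say on whether an event is progression (SAP 8.5).

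**The concern.** A time-to-event endpoint should be ascertained in the same way in both arms. Here, a patient whose FEV1 first falls at Visit 9 has a scheduled opportunity for confirmation if he or she stays out of BOSTON-3, and none within BOSTON-1 otherwise. Censoring at study termination also falls about 4 weeks earlier in entrants.

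Entry is decided after randomization and with the arm known. Within this programme, SoC patients obtain L-CsA through BOSTON-3, while L-CsA patients would be continuing it, so entry rates could differ in either direction. Entry could also depend on how the patient has done. In either case, the Visit 9 events that survive confirmation would differ for reasons other than treatment, and the curves and hazard ratio for progression would carry that difference.

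**Working it through.** **1. The plan's own figure.** No event count or power for progression is visible. The only sample-size figure concerns FEV1 (SAP 8.2): n = 2(1.960 + 0.842)²(350/200)² = 48.1, so 49 per arm against the 50 stated; noncentral-t power at 50 is 0.808. It reproduces, but does not bear on progression.

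**2. Timing.** SAP Table 1 puts Visit 9 at day 337 and Visit 10 at day 365. The gap is 365 − 337 = 28 days, which exceeds the 14 needed, so Visit 10 can confirm a Visit 9 fall. An FEV1 fall first seen at Visit 10 has no later scheduled visit in anyone.

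**3. Events first seen at Visit 9.** SAP 8.2 gives 62 randomized; at 1:1 this is taken as 31 per arm. The risk p by Week 48 is an assumption, 30-50%. The upper end echoes the 50% control success rate in study AI001 (5 of 10, Protocol 7.1.4), and reading that as a 48-week risk is itself an assumption. With a constant hazard, S(t) = (1 − p)^(t/48), and the share first seen at Visit 9 is [S(40) − S(48)] / [1 − S(48)].

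| p | S(40) | S(40) − S(48) | Share of events | Events per arm (31 × p × share) |
|---|---|---|---|---|
| 30% | 0.743 | 0.043 | 0.143 | 1.3 |
| 40% | 0.653 | 0.053 | 0.133 | 1.65 |
| 50% | 0.561 | 0.061 | 0.122 | 1.9 |

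**4. Expected difference between arms.** If entry differs by 20 percentage points, the confirmable Visit 9 events differ by 0.20 × 1.3 to 0.20 × 1.9, about 0.3-0.4 events. At 45 points the difference is 0.45 × 1.3 to 0.45 × 1.9, about 0.6-0.9.

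**5. Effect on the comparison.** This was simulated with no treatment effect: 31 per arm, exponential onset, visits at Weeks 4, 8, 12, 16, 24, 32, 40, 48 and 52, and 4000 runs per scenario. Visit 9 falls count only in non-entrants, falls first seen at Visit 10 count in nobody, and entry is unrelated to prognosis. Entry rates are assumptions.

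| Entry, L-CsA v SoC | p | Confirmed events, L-CsA v SoC | HR | One-sided error favouring L-CsA |
|---|---|---|---|---|
| 80% v 80% | 30% | 8.28 v 8.24 | 1.006 | 2.25% |
| 80% v 80% | 50% | 14.01 v 13.98 | 1.003 | 2.15% |
| 90% v 70% | 30% | 8.14 v 8.34 | 0.978 | 2.65% |
| 90% v 70% | 50% | 13.77 v 14.15 | 0.972 | 2.80% |
| 95% v 50% | 30% | 8.01 v 8.64 | 0.925 | 3.38% |
| 95% v 50% | 50% | 13.69 v 14.57 | 0.934 | 3.57% |

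Reversing the rates gives HRs of about 1.03 (70% v 90%) and 1.08 (50% v 95%). The Monte Carlo standard error at 2.5% is √(0.025 × 0.975/4000) = 0.25 percentage points. The error rates at 90% v 70% are therefore indistinguishable from nominal, and those at 95% v 50% are not. Under one common rule, with follow-up ended at Visit 9 and Visit 9 falls counted in everyone, events are about 9.3 in each arm at 30% and 15.5 at 50%.

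**The case against.** The strongest reply is the redaction. SAP 14.3.2 was clarified on this very topic and may set a censoring date, a rule for an unconfirmed Visit 9 fall, or use of BOSTON-3 spirometry. That stands: nobody can say from the public text that such a rule is missing, so the request must be conditional.

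A reader might infer that entrants have no spirometry after Visit 9 and cannot be confirmed. The documents do not support that. Unscheduled visits are allowed (Protocol 14.2.7) and their measurements are mapped to visits (SAP 9.4). Entrants' data count under Visit 9 up to day 385, and neither document ties confirmation to the next scheduled visit. What is missing for entrants is a scheduled opportunity. Nor is staying out of BOSTON-3 always a refusal.

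A reader might also infer that Visit 10 gives non-entrants a run of extra progressions. For FEV1 falls it does not, since nobody has a later scheduled visit to confirm them. A grade worsening at Visit 10 could count at once if the protocol's wording governs, but not if SAP 7.1 governs.

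Unequal follow-up alone does not bias a log-rank comparison; entry must differ by arm or relate to prognosis, and the documents give no entry rates. The change is disclosed in SAP section 16, and the protocol lets the final SAP govern. Counting events after treatment discontinuation also fits the instruction to keep following such patients. Section 14 of the SAP calls all analyses descriptive, and the protocol synopsis confines the hierarchy for time to progression to BOSTON-2. All of this limits the consequence. It does not remove the dependence on entry, and SAP 14.5 still compares progression curves by log-rank test within subgroups.

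**Conclusion.** The visible text makes scheduled confirmation of a Visit 9 fall depend on BOSTON-3 entry, an open-label post-randomization step. The likely distortion is modest: about 1.3-1.9 events per arm are exposed to it, with a null HR of about 0.97-0.98 at 90% versus 70% entry and about 0.93 only at the extreme 95% versus 50%. The direction depends on which arm enters more, so the documents do not support saying that the rule favours L-CsA.

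These sizes rest on an assumed 30-50% risk, a constant hazard, assumed entry rates, entry unrelated to prognosis, and every progression needing confirmation. If entry relates to prognosis, the distortion could be larger or smaller. If grade worsening, re-transplantation and respiratory death need no confirmation, fewer Visit 9 events are affected. No confirmatory claim in this study rests on the endpoint. The point merits a change because the remedy is cheap and an arm may have only about 9-16 progressions.

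**What to change.** Unless SAP 14.3.2 already does so:

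- Add a prespecified time-to-progression analysis that stops follow-up at Week 48 (the Visit 9 window) for every patient. Use one upper limit for all: SAP Table 1 ends that window at day 364 for non-entrants and day 385 for entrants, which would bring the dependence back. The protocol's own limit, Week 48 plus 14 days (Week 50), precedes the earliest in-window Visit 10 (Week 52 minus 7 days, Week 51).
- Keep every event confirmed before the cut, including those of early withdrawers, whose end-of-treatment and final visits may both fall before Week 48 (Protocol 10.3.1). Dropping all Visit 9 falls and all Visit 10 data would delete valid events.
- Apply one rule, regardless of BOSTON-3 entry, to Visit 9 falls not confirmed by the cut: counted for all patients in one run and for none in the other.
- Report BOSTON-3 entry by arm, and list later events separately.
- Reconcile Protocol 12.1.2 with SAP 7.1 on which components need confirmation.

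The cost is SAP wording and one or two extra runs on data already collected. The downside is that a few events confirmed at Visit 10 are handled differently from the current rule.
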